4.3. Randomization Criteria

A subject who has signed an informed consent document to participate in the study, has undergone all screening procedures, and has met all inclusion and none of the exclusion criteria for participation in the study at the Baseline visit.

4.4. Lifestyle Requirements

In order to participate in the study, subjects must be made aware of the following lifestyle guidelines and restrictions that apply during the study period. Details of these life style guidelines are provided in the sections as noted.

- On designated study visit days, comply with fasting requirements for at least 9 hours prior to visit (See [Section 6](#)). On study visit days, subject should not take the in-clinic dose of study medication before the clinic visit.
- On study visit days, do not smoke or ingest caffeine (eg, tea, coffee, some soft drinks/colas/energy drinks and power bars) during the 30 minutes prior to blood pressure and pulse (heart) rate measurements.
- On study visit days, take prescribed permitted concomitant medication, as needed, prior to the study visit, if it can be administered with water only.
- Avoid vaccinations with live or attenuated live vaccines and contact with individuals who have recently received live or attenuated live vaccines (See [Section 4.4.4](#)).
- Discontinue and avoid using certain medications and treatments (see [Inclusion Criteria](#) and list of prohibited medications in [Section 5.8.4](#) and [Appendix 4](#)).
- Contact the study site investigator if there are any changes or additions to concomitant medications.
- Avoid having elective surgery (See [Section 4.4.5](#)).
- Agree to use highly effective contraceptive methods per [Section 4.4.6](#).

4.4.1. Fasting Visit Requirements

On visit days when fasting lipid panels are scheduled to be collected, all subjects should refrain from all food and liquids (water and regular medications permitted; [REDACTED] [REDACTED]) for at least 9 hours prior to scheduled safety laboratory tests. Visits that require fasting are Baseline/Day 1, Weeks 4, 16, 32, 48 and Follow-up.

4.4.2. Non-Pharmacologic Interventions

The subject should continue all non-pharmacological therapies, such as physical therapy, as indicated. However, the subject should avoid changing the type or intensity of therapy, or initiating new therapy, until after the Week 16 visit.

4.4.3. Dietary Supplements

For the purposes of this protocol, dietary supplements are defined as vitamins, minerals, purified food substances, and herbals with pharmaceutical properties.

Vitamins, minerals and purified food substances are allowed in amounts not known to be associated with adverse effects (such as hypervitaminosis). Herbals with pharmaceutical properties are allowed only if there is acceptable evidence of no CYP3A inhibition or induction. Otherwise, herbals with pharmaceutical properties must be discontinued for at least 4 weeks prior to first dose of investigational product, unless there is sufficient data

available regarding the duration of an herbal medication's pharmacokinetic and pharmacodynamic effects to allow a shorter washout to be specified (eg, 5 half-lives). Please direct any questions to the Sponsor.

Glucosamine sulfate and chondroitin sulfate are allowed in the study but subjects should be on a stable dose for 1 week prior to first dose of investigational product and throughout the study.

4.4.4. Vaccine Guidelines

Vaccination with live or live attenuated components is prohibited during the study and for 6 weeks after last dose of investigational product. Similarly, current routine household contact with children and others vaccinated with live vaccine components should be avoided during treatment and for 6 weeks following completion of the study. Some of these vaccines include varicella ("chickenpox or shingles") vaccine, oral polio vaccine, and the inhaled flu vaccine. Following vaccination with live component vaccines, the virus may be shed in bodily fluids, including stool, and there is a potential risk that the virus may be transmitted. General guidelines suggest that exposure should be avoided following vaccination with these vaccines for the stated time period:

- Varicella or attenuated typhoid fever vaccination for 4 weeks following vaccination;
- Oral polio vaccination for 6 weeks following vaccination;
- Attenuated rotavirus vaccine for 10 days following vaccination;
- FluMist[®] (inhaled flu vaccine) for 1 week following vaccination.

4.4.5. Elective Surgery

During the course of this study, elective surgery should be delayed until the end of the placebo-controlled period. No elective surgery should be scheduled without first consulting with the Pfizer Medical Monitor.

Subjects who do require surgery should temporarily discontinue investigational product for one week prior to the surgical procedure and remain off investigational product after the surgical procedure until sutures/staples are removed. If absorbing sutures or chemical closure methods are utilized, investigational product can be resumed when the operative site is sufficiently healed and risk of infection is minimal.

4.4.6. Contraception

The investigator or his or her designee, in consultation with the subject, will confirm that the subject has selected an appropriate method of contraception for the individual subject and his/her partner(s) from the permitted list of contraception methods (see below) and will confirm that the subject has been instructed in its consistent and correct use. At time points indicated in the [Schedule of Activities](#), the investigator or designee will inform the subject of the need to use highly effective contraception consistently and correctly and document the

conversation, and the subject's affirmation, in the subject's chart (subjects need to affirm their consistent and correct use of at least 1 of the selected methods of contraception). In addition, the investigator or designee will instruct the subject to call immediately if the selected contraception method is discontinued or if pregnancy is known or suspected in the subject or partner. Subjects in Canada who are women of childbearing potential (WOCBP) and sexually active are required to use two contraceptive methods at the same time, one highly effective contraceptive method and one additional effective contraceptive method.

A female subject is eligible to participate if she is not pregnant or breastfeeding, and at least 1 of the following conditions applies:

- Is not a woman of childbearing potential (WOCBP).

OR

- Is a WOCBP and using a contraceptive method that is highly effective (with a failure rate of <1% per year), preferably with low user dependency, as described below during the intervention period and for at least 28 days after the last dose of study intervention, which corresponds to the time needed to eliminate any study intervention(s). The investigator should evaluate the effectiveness of the contraceptive method in relationship to the first dose of study intervention.

The investigator is responsible for review of medical history, menstrual history, and recent sexual activity to decrease the risk for inclusion of a woman with an early undetected pregnancy.

Highly effective methods of contraception are those that, alone or in combination, result in a failure rate of less than 1% per year when used consistently and correctly (ie, perfect use) and include the following:

Highly Effective Methods That Have Low User Dependency

1. Implantable progestogen-only hormone contraception associated with inhibition of ovulation.
 2. Intrauterine device (IUD).
 3. Intrauterine hormone-releasing system (IUS).
 4. Bilateral tubal occlusion.
 5. Vasectomized partner.
- Vasectomized partner is a highly effective contraceptive method provided that the partner is the sole sexual partner of the WOCBP and the absence of sperm has been confirmed. If not, an additional highly effective method of contraception should be used. The spermatogenesis cycle is approximately 90 days.

Highly Effective Methods That Are User Dependent

1. Combined (estrogen- and progestogen-containing) hormonal contraception associated with inhibition of ovulation:
 - Oral;
 - Intravaginal;
 - Transdermal;
 - Injectable.
2. Progestogen-only hormone contraception associated with inhibition of ovulation:
 - Oral;
 - Injectable.
3. Sexual abstinence:
 - Sexual abstinence is considered a highly effective method only if defined as refraining from heterosexual intercourse during the entire period of risk associated with the study intervention. The reliability of sexual abstinence needs to be evaluated in relation to the duration of the study and the preferred and usual lifestyle of the participant.

Effective methods may include barrier methods of contraception (eg, male condom, female condom, cervical cap, diaphragm or contraceptive sponge). The proper use of diaphragm or cervical cap includes use of spermicide and is considered one barrier method.

No effects of tofacitinib have been seen in male fertility or offspring of dosed males in any preclinical studies conducted to date. However, male subjects who are on background medications (including DMARDs) that require male contraceptive precautions according to the local drug label must do so if they are sexually active with women of child bearing potential during the study and after therapy for 3 months or for the duration specified in the local drug label. Subjects who are receiving concomitant drugs (eg, methotrexate) that require contraceptive precautions in their labeling should follow the most stringent precautions.

4.4.7. Sponsor's Qualified Medical Personnel

The contact information for the sponsor's appropriately qualified medical personnel for the trial is documented in the study contact list located in the study team repository site.

To facilitate access to appropriately qualified medical personnel on study-related medical questions or problems, subjects are provided with a contact card. The contact card contains, at a minimum, protocol and investigational product identifiers, subject study numbers, contact information for the investigator site, and contact details for a contact center in the event that the investigator site staff cannot be reached to provide advice on a medical question or problem originating from another healthcare professional not involved in the subject's participation in the study. The contact number can also be used by investigator staff if they are seeking advice on medical questions or problems; however, it should be used only in the event that the established communication pathways between the investigator site and the study team are not available. It is therefore intended to augment, but not replace, the established communication pathways between the investigator site and the study team for advice on medical questions or problems that may arise during the study. The contact number is not intended for use by the subject directly, and if a subject calls that number, he or she will be directed back to the investigator site.

5. STUDY TREATMENTS

For the purposes of this study, and per International Council for Harmonisation (ICH) guidelines, investigational product is defined as a pharmaceutical form of an active ingredient or placebo being tested or used as a reference/comparator in a clinical trial, including a product with a marketing authorization when used or assembled (formulated or packaged) in a way different from the approved form, or when used for an unapproved indication, or when used to gain further information about an approved use (ICH E6 1.33).

For this study, the investigational products are tofacitinib and placebo.

5.1. Allocation to Treatment

Allocation of subjects to treatment groups will proceed through the use of an interactive response technology (IRT) system (interactive Web-based response [IWR]). The site personnel (study coordinator or specified designee) will be required to enter or select information including but not limited to the user's identification (ID) and password, the protocol number, patient population (bDMARD-naïve or TNFi-IR or bDMARD use [non-IR]) and the subject number. The site personnel will then be provided with a treatment assignment, randomization number, and dispensable unit (DU) or container number when investigational product is being supplied via the IRT system. The IRT system will provide a confirmation report containing the subject number, randomization number, and DU or container number assigned. The confirmation report must be stored in the site's files.

The study-specific IRT reference manual will provide the contact information and further details on the use of the IRT system.

Subjects will be randomized at the Baseline visit in a 1:1 ratio to one of the following two parallel blinded treatment sequences for a total of 16 weeks of treatment. Eligible subjects will be treated with one of the two sequences for 16 weeks followed by treatment with tofacitinib 5 mg BID for an additional 32 weeks.

Randomization will be stratified by prior treatment history: (1) bDMARD-naive and (2) TNFi-IR or bDMARD use (non-IR). During the feasibility phase of clinical trial preparation, the sponsor conducted a survey of the countries and sites likely to participate in the study. While there was country-to-country variability, the overall proportion of bDMARD-naïve and TNFi-IR or bDMARD use (non-IR) was approximately 80%/20% respectively. The clinical trial was thus designed to reflect this prevalence. Subjects with more than 2 TNFi failures were excluded due to the higher likelihood that they could be refractory to tofacitinib therapy, an observation noted in other tofacitinib trials in RA and PsA.

Strata (Patient Population)	Sequence	Treatment Sequence and Description	Planned Number of Randomized Subjects
bDMARD-naive	1	Blinded Tofacitinib 5 mg BID for 16 weeks followed by open-label tofacitinib for 32 weeks One-tofacitinib 5 mg tablet in AM & PM	96
bDMARD-naive	2	Placebo BID for 16 weeks followed by open-label 5 mg BID tofacitinib for 32 weeks One- 5 mg matching placebo tablet in AM & PM for the first 16 weeks followed by one-tofacitinib 5 mg tablet in the AM & PM for 32 weeks	96
TNFi-IR or bDMARD use (non-IR)	1	Blinded Tofacitinib 5 mg BID for 16 weeks followed by open-label tofacitinib for 32 weeks One-tofacitinib 5 mg tablet in AM & PM	24
TNFi-IR or bDMARD use (non-IR)	2	Placebo BID for 16 weeks followed by open-label 5 mg BID tofacitinib for 32 weeks One- 5 mg matching placebo tablet in AM & PM for the first 16 weeks followed by one-tofacitinib 5 mg tablet in the AM & PM for 32 weeks	24

At the end of the 16 week double-blinded treatment period, all subjects will be assigned to open-label tofacitinib 5 mg BID to Week 48. The investigators, subjects and sponsor study team will remain blinded to the first 16 weeks of treatment assignment through the entire duration of the trial until database release.

5.2. Breaking the Blind

This study will be subject-, investigator-, and sponsor-blinded. For the open-label treatment period, subjects, investigator and sponsor study team will remain blinded to the double-blind treatment period study sequence.

At the initiation of the study, the investigator site will be instructed on the method for breaking the blind. The method will be an electronic process. Blinding codes should be broken only in exceptional circumstances when knowledge of the actual treatment code is absolutely essential for further management of the subject. Investigators are encouraged to discuss with a member of the study team if they believe that unblinding is necessary. When the blinding code is broken, the reason must be fully documented and entered on the electronic case report form (eCRF).

5.3. Subject Compliance

Subject compliance with dosing administration will be verified by accounting of returned containers and investigational product at each visit. Compliance for the tablets will be calculated by each bottle and documented. If compliance is <80%, the investigator or designee is to counsel the subject and ensure steps are taken to improve compliance. Subjects, who are less than 80% compliant with the dosage regimen for any two consecutive visit periods, should be withdrawn from the investigational product. In the event that the investigational product is held due to an AE, infection or elective surgery, in accordance with the protocol-specified time frames, compliance should still be calculated for the visit period, but withdrawal from the investigational product would be assessed. If the subject is over-compliant with the investigational product (intentional or accidental) the investigator or designee is to counsel the subject and ensure correct understanding of the investigational product dosing regimen. The investigator should contact the Pfizer Medical Monitor or designee promptly with any over-compliance (>120%) that may potentially impact the safe use of the investigational product or that may result in a serious adverse event.

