5.5. Administration

Investigational product will be dispensed to subjects to self-administer after appropriate training and specific instructions are provided. Instructions on dosing will be provided on the Subject Dosing Card. At all visits, the scheduled dose of investigational product will be taken by the subject in the clinic. At the end of each visit, sites will instruct subjects, when to take their investigational product prior to their next study visit. [REDACTED]

[REDACTED] Subjects should receive open-label investigational product at the Week 16 visit and should receive the first dose of the open-label investigational product at the clinic.

Tofacitinib tablets or matching placebo for oral administration may be taken with or without food. Subjects will swallow the investigational product whole, and will not manipulate or chew the investigational product prior to swallowing.

Subjects will be instructed to take their tablet investigational product twice daily (once in the morning and once in the evening approximately 12 hours apart) for a total of two tablets per day. Placebo tablets will match the 5 mg tablets in order to maintain the blind.

During the double-blind treatment period, if the investigator deems it necessary to withhold the investigational product to treat a non-serious infection or other medical condition, temporary withholding is permitted for up to 5 days. If temporary withholding of the investigational product exceeding 5 days is required for a medical reason (eg, elective surgery), the investigator must contact the Pfizer Medical Monitor for approval.

Temporary withholding of the investigational product, as described above, is permitted once during the study without obtaining prior approval from the Pfizer Medical Monitor. Any additional request(s) for temporary withholding of the investigational product during the double blind period require(s) documented approval by the Pfizer Medical Monitor.

Per Amendment 3, for subjects with suspected VTE, treatment with tofacitinib should be temporarily withheld while the subject is evaluated. If VTE is confirmed, discontinue treatment with tofacitinib (see Section 6.4: Subjects Discontinuation from the Investigational Product).

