During the open-label period of the study, tofacitinib 5 mg BID may be temporarily discontinued for up to 28 consecutive days for laboratory abnormalities, for infections which do not meet criteria for serious infections (those requiring parenteral antimicrobial therapy or hospitalization), for surgical procedures or other moderately severe AEs. If treatment must be discontinued for more than 28 days, the subject should be withdrawn from the investigational product permanently (see [Section 6.4.2](#)).

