6.4.2. Discontinuation Criteria (from the Investigational Product)

The investigational product will be discontinued in the event of any of the following:

- Serious infections, defined as any infection (viral, bacterial, and fungal) requiring parenteral antimicrobial therapy or hospitalization for treatment, or meeting other criteria that require the infection to be classified as a serious adverse event;
- Two sequential absolute neutrophil counts $<1.0 \times 10^9/L$ ($<1000/mm^3$);
- Two sequential absolute lymphocyte counts <500 lymphocytes/ mm^3 ;
- Two sequential hemoglobin values <8.0 g/dL (80 g/L) or decreases of $>30\%$ from baseline value;

- Two sequential platelet counts $<75 \times 10^9/L$ ($<75,000/mm^3$);
- Two sequential AST or ALT elevations ≥ 3 times the upper limit of normal with at least one total bilirubin value ≥ 2 times the upper limit of normal;¹
- Two sequential AST or ALT elevations ≥ 3 times the upper limit of normal accompanied by signs or symptoms consistent with hepatic injury (eg, new onset elevated PT/INR);¹
- Two sequential AST or ALT elevations >5 times the upper limit of normal, regardless of total bilirubin or accompanying signs or symptoms;¹
- Two sequential increases in serum creatinine $>50\%$ AND an absolute increase in serum creatinine >0.5 mg/dL ($44 \mu\text{mol/L}$) over the average of screening and baseline values;
- Two sequential creatine kinase (CK) elevations >10 times the upper limit of normal, unless the causality is known not to be medically serious (eg, exercise or trauma induced);
- A confirmed positive urine pregnancy test in a woman of childbearing potential;
- Any opportunistic infections considered significant by the investigator or the Sponsor;
- Requirement of rescue medication for more than 10 consecutive days;
- Subjects interrupting investigational product for more than 5 consecutive days during the double-blind portion or 28 consecutive days during the open-label treatment period or subjects who are less than 80% compliant with the dosage regimen for any two consecutive visit periods;
- Other serious or severe adverse events, in the opinion of the investigator or sponsor. Whenever possible, the investigator should consult with a member of the study team before discontinuation of the subject from the investigational product;
- If VTE is confirmed, discontinue treatment with tofacitinib.

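### Protocol 6.4.2 makes stopping mandatory below 80% compliance in two consecutive visit periods, with no exception for holds that 5.5 permits and 5.3 leaves to assessment

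*Protocol*

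**What the plan says.** Protocol 5.3 gives a general rule that a subject below 80% compliance in two consecutive visit periods should come off product. It then treats holds for an adverse event, infection or elective surgery differently, provided they stay within the protocol's time frames: "compliance should still be calculated for the visit period, but withdrawal from the investigational product would be assessed".

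Protocol 6.4.2 opens its list with "The investigational product will be discontinued in the event of any of the following". One bullet in that list covers two things: "Subjects interrupting investigational product for more than 5 consecutive days during the double-blind portion or 28 consecutive days during the open-label treatment period", and "subjects who are less than 80% compliant with the dosage regimen for any two consecutive visit periods". The bullet has no exception for permitted holds and no reference to 5.3.

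Protocol 5.5 sets out the permitted holds:

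- **Open label:** product "may be temporarily discontinued for up to 28 consecutive days for laboratory abnormalities, for infections which do not meet criteria for serious infections", and also for surgical procedures or other moderately severe adverse events. Permanent withdrawal is required only past that limit: "If treatment must be discontinued for more than 28 days, the subject should be withdrawn from the investigational product permanently". The reference given there is to 6.4.2.
- **Double blind:** up to 5 days, once without prior approval. Any further hold needs documented Medical Monitor approval. Approval is also needed when "temporary withholding of the investigational product exceeding 5 days is required for a medical reason".

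Protocol 4.4.5 adds that subjects who need surgery stop one week beforehand and "remain off investigational product after the surgical procedure until sutures/staples are removed".

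**The concern.** One section leaves withdrawal to judgement after a permitted hold; another requires it. A site that follows 5.5 to 6.4.2, as directed, never meets the softer wording in 5.3 and could permanently stop a subject whose interruption the protocol allows.

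Two things are at stake. The subject loses study drug without a clinical reason. And because SAP 9.1 limits on-drug data to visits on or before permanent discontinuation, and SAP 5.3 sets missing binary responses to non-response, the subject becomes a non-responder at every later visit in the on-drug binary analyses. Before Week 16 that includes the primary analysis, since Estimand 1 (SAP 2.1.1) counts discontinuation of product as non-response.

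**Working it through.** The plan states no figure on this point, so the check is a dose count.

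**Inputs.** Two tablets a day (Protocol 5.5). Open-label visits at Weeks 16, 24, 32, 40 and 48, so 56 days or 112 doses per period, with ±7-day windows (Schedule of Activities). Double-blind visits at Weeks 2 and 4 (±3 days) and 8, 12 and 16 (±7 days). Compliance = doses taken / doses expected (SAP 4.2.3). Held doses are assumed to stay in the expected count, and all other doses are assumed taken.

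**Open-label threshold.** (112 − m)/112 < 0.80 requires m > 22.4, so m = 23 missed doses (11.5 days). Check: 90/112 = 80.4%, not caught; 89/112 = 79.5%, caught.

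**Shortest single hold.** Both adjacent periods must fall below 80%: 23 + 23 = 46 doses = 23 days. In whole days it is 12 + 12 = 24, because 45/56 = 80.4% and 44/56 = 78.6%. The longest permitted hold, 28 days split 14/14, gives 84/112 = 75.0% in both periods. Two separate 12-day holds in adjacent periods give 88/112 = 78.6% each.

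**Visit windows.** Two 49-day periods (98 doses) need 20 missed in each (78/98 = 79.6%), so 20 days. Two 63-day periods (126 doses) need 26 in each (100/126 = 79.4%), so 26 days. The minimum triggering hold therefore ranges from 20 to 26 days.

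**What follows from each straddle.**

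- Across Week 24: rule met at Week 32. Up to 16 weeks of drug lost; on-drug results at Weeks 40 and 48 affected.
- Across Week 32: rule met at Week 40. Up to 8 weeks lost; Week 48 affected.
- Across Week 40: rule met at Week 48, when dosing ends. No effect.

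**How few positions qualify.** A hold of L days has 2L doses, with at least 23 on each side of the visit, so 2L − 45 half-day start times qualify per visit. The 32 open-label weeks contain 224 × 2 = 448 start times, and two visits matter:

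- L = 23: 2 × 1/448 = 0.4%
- L = 25: 2 × 5/448 = 2.2%
- L = 28: 2 × 11/448 = 4.9%

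If only start times from which a 28-day hold can finish by Week 48 are counted (448 − 56 + 1 = 393), the last figure is 22/393 = 5.6%.

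**Double blind, one hold.** To be below 80% in both periods, the missed doses must exceed 20% of the pair's total. The shortest possible pair is Baseline to Week 4 at 25 days, or 50 doses, so at least 11 must be missed. A 5-day hold misses 10. It cannot trigger the rule.

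**Double blind, two holds.** Three days in Baseline–Week 2 and three in Weeks 2–4 miss 6 of 28 doses in each: 22/28 = 78.6% twice. Neither hold exceeds 5 days, so the interruption limit is not breached, and 5.5 allows the second with approval. The compliance rule is met at Week 4.

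**The case against.** The best defence is that 5.3 already handles the case. The 6.4.2 bullet restates the 5.3 rule almost verbatim, and in 5.3 the very next provision says what to do after a permitted hold. A specific provision would ordinarily qualify the general one, and the same bullet gives interruptions their own limits. This is probably what was intended. It is not what 6.4.2 says, though: its list is mandatory, its creatine kinase criterion shows that exceptions are written in where wanted, and 5.5 sends the reader there rather than to 5.3.

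The denominator objection also has force. Neither document says whether doses held on instruction remain expected. The instruction in 5.3 to go on calculating compliance through a hold supports that reading without settling it.

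Three stronger readings are tempting and should be resisted.

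- A reader might infer that any open-label hold of 23 to 28 days forces discontinuation. It does not: the hold must straddle a visit nearly evenly, and few start times qualify.
- A reader might infer that 5.3 and 5.5 list different permitted reasons, because 5.5 names laboratory abnormalities and surgical procedures. That is weak. The closing words of the 5.5 list treat the earlier items as adverse events, and 8.2.1 and 8.2.2 make many abnormal test findings adverse events, so 5.3 largely covers them.
- A reader might infer a material threat to the Week 16 result. The documents support only an uncommon route through two separate holds. The opposite inference, that the double-blind period is wholly immune, fails as well, because 5.5 allows an approved further hold.

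**Conclusion.** Wrong as written, and minor. A mandatory stopping rule can catch subjects whose holds the protocol permits.

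For open-label holds the effect is confined to on-drug results at Weeks 40 and 48, or Week 48 alone. Those results are secondary, stopped subjects stay in follow-up (Protocol 6.4), and ASAS20 and ASAS40 are also reported on on-study data. In the double-blind period the two-hold case would make a subject a Week 16 non-responder in the primary on-drug analysis. This should be rare; the documents give no frequency of long or repeated holds.

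The figures rest on held doses counting as expected, all other doses being taken, and nominal spacing except where windows are stated. The double-blind example also treats Baseline–Week 2 and Weeks 2–4 as separate visit periods. That fits drug accountability at both visits, but 5.3 also speaks of calculating by bottle and nothing is dispensed at Week 2. On a bottle basis the same two holds give 44/56 = 78.6% in one period only, and the rule is not met. Holds running across Week 16 are not counted above. At nominal spacing, 5 days before that visit leaves 46/56 = 82.1%, so they are not caught.

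**What to change.** In the 6.4.2 compliance criterion add: *except where the shortfall is due to product withheld in accordance with Section 4.4.5 or 5.5, in which case withdrawal is assessed by the investigator with the Medical Monitor (see Section 5.3)*. The clause should apply to both the double-blind and the open-label period.

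The 5-day and 28-day interruption limits in 6.4.2 stay as they are, so a double-blind interruption longer than 5 days still meets that separate criterion. Adding laboratory abnormalities and surgery to the 5.3 list is optional. The per-protocol exclusion for low compliance in SAP 4.2.3 is a separate analysis choice and is not altered by this clause.

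The cost is one clause in the protocol.
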